12.1 Analysis sets

The Randomized Analysis Set (RAS) consists of all randomized subjects. Subjects will be analyzed according to the treatment assigned to at randomization.

The Full Analysis Set (FAS) comprises all subjects to whom study treatment has been assigned. Subjects will be analyzed according to the treatment assigned to at randomization. Mis-randomized subjects (mis-randomized in IRT) will be excluded from FAS. Mis-randomized subjects are defined as cases where IRT contacts were made by the site either prematurely or inappropriately prior to confirmation of the subject's final randomization eligibility and no study medication was administered to the subject.

The Safety Set includes all subjects who received at least one dose of study treatment. Subjects will be analyzed according to the study treatment received, where treatment received is defined as the randomized/assigned treatment if the patient took at least one dose of that treatment or the first treatment received if the randomized/assigned treatment was never received.

For all analysis in Treatment Period 1, the Placebo group to secukinumab 300 mg every 2 weeks and Placebo group to secukinumab 300 mg every 4 weeks will be pooled together.

12.2 Subject demographics and other baseline characteristics

The analysis of subject demographics and other baseline characteristics data will be based on Randomized Analysis Set.

Demographics and baseline characteristics

Summary statistics will be presented for continuous demographic and baseline characteristic variables for each treatment group and for all subjects. The number and percentage of subjects in each category will be presented for categorical variables for each treatment group and for all subjects.

Medical history

Any condition entered as medical history or current medical conditions at baseline will be coded using the MedDRA dictionary. Medical history will be summarized by system organ class and preferred term in the MedDRA dictionary.

12.3 Treatments

The analysis of study treatment data will be based on the Safety Set.

The number of active and placebo injections will be summarized by treatment group by means of contingency tables.

The duration of exposure to study treatment will also be summarized by treatment group. In addition, the number of subjects with exposure of at least certain thresholds (e.g., any exposure, ≥ 1 week, ≥ 2 weeks, ≥ 3 weeks, ≥ 4 weeks, ≥ 8 weeks, etc.) will be displayed.

Prior and concomitant treatments

Prior and concomitant treatments will be summarized by treatment group in separate tables for the Safety Set.

Prior treatments are defined as treatments taken and stopped prior to first dose of study treatment. Any treatment given at least once between the day of first dose of randomized study treatment and the last day of study visit will be a concomitant treatment, including those that were started pre-baseline and continued into the treatment period.

Treatments will be presented in alphabetical order, by ATC codes and main groups. Tables will also show the overall number and percentage of subjects receiving at least one treatment of a particular ATC code and at least one treatment in a particular anatomical main group.

In addition, medical procedures and significant non-drug therapies as coded in MedDRA will be summarized.

12.4 Analysis of the primary endpoint(s)

The primary aim of the study is to demonstrate the efficacy of two secukinumab regimens compared to placebo with respect to HiSCR after 16 weeks of treatment. The detailed definition and the justification of the corresponding primary Estimand, as well as the definition of the supplementary Estimands will be provided in the Statistical Analysis Plan.

12.4.1 Definition of primary endpoint(s)

The primary endpoint of the study is HiSCR at Week 16, defined as at least a 50% decrease in Abscess and inflammatory Nodule (AN) count compared to baseline with no increase in the number of abscesses and/or in the number of draining fistulas from baseline to Week 16. The baseline is defined as the last assessment (including unscheduled visits) obtained before/on the day of the first administration of the study treatment, or on the randomization date if there has been no drug administration.

The analysis of the primary endpoint will be based on the FAS.

12.4.2 Statistical model, hypothesis, and method of analysis

The statistical hypotheses for the primary endpoint being tested is that there is no difference in the proportion of HiSCR at Week 16 in any of the secukinumab regimens versus placebo regimen.

Let p_j denote the proportion of HiSCR at Week 16 for treatment regimens j , $j = 0, 1, 2$ where

- 0 corresponds to placebo regimen,
- 1 corresponds to secukinumab 300 mg q2w s.c.,
- 2 corresponds to secukinumab 300 mg q4w s.c.,

In statistical terms, $H_j: p_j = p_0, H_{A_j}: p_j \neq p_0$ for the j th secukinumab regimen, i.e.

H_1 : secukinumab 300 mg q2w s.c. is not different to placebo regimen with respect to HiSCR after 16 weeks of treatment.

H_2 : secukinumab 300 mg q4w s.c. is not different to placebo regimen with respect to HiSCR after 16 weeks of treatment.

The primary analysis method will be logistic regression with treatment group, geographical region, Hurley stage, use of antibiotic, baseline body weight and baseline AN counts as explanatory variables. Odds ratios will be computed for comparisons of secukinumab dose regimens versus placebo utilizing the logistic regression model fitted. In case of response rates of 0% or of 100% in one of the treatment groups, Fisher's exact test will be applied. Risk difference and confidence intervals for risk difference will be provided.

The detailed testing strategy including the primary endpoint analysis is provided in [Section 12.5](#). Efficacy of two secukinumab regimens compared to placebo with respect to HiSCR after 16 weeks of treatment could be demonstrated if H_1 and/or H_2 is/are rejected and the treatment effect is in favor of secukinumab.

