
• To explore the efficacy of secukinumab compared to placebo with respect to HiSCR response after 16 weeks of treatment and the sustained efficacy over time in bio-naïve patients.• To explore the efficacy of secukinumab compared to placebo with respect to HiSCR response after 16 weeks of treatment and the sustained efficacy over time in patients with body weight lower and higher than 90 kg (<90 kg and ≥90 kg).	
• Achievement of HiSCR at Week 16 and up to Week 52 in bio-naïve patients.• Achievement of HiSCR at Week 16 and up to Week 52 in patients with body weight lower and higher than 90 kg (<90kg and ≥90kg).

3 Study design

This is a multicenter, randomized, double-blind, placebo controlled, parallel group study with two secukinumab dose regimens in approximately 541 patients with moderate to severe HS.

The study consists of: Screening (up to 4 weeks), Treatment Period 1 (16 weeks) and Treatment Period 2 (36 weeks). Subjects who prematurely discontinue the study, or who complete the study and cannot or do not wish to continue in a planned optional extension study, will need to complete a post-treatment Follow-Up period (8 weeks).

Safety, efficacy, biomarker and pharmacokinetic measurements of secukinumab will be assessed.

An outline of the study design is presented in [Figure 3-1](#), and a detailed visit and assessment schedule is provided in [Table 8-1](#).

Screening (Screening to Randomization)

A screening period of up to 4 weeks will be used to assess the subject's eligibility and to washout and/or taper prohibited medication(s). Two screening visits will be performed: Visit 1 (Day -28 to Day -14) and Visit 2 (Day -13 to Day -1). Subjects can be re-screened if the subject screen fails due to a transient medical condition or due to an insufficient prohibited medication washout period. Subjects can be re-screened only once and no study-related re-screening procedure should be performed prior to re-consenting the subject.

Important note:

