Days	-28 to -14	-13 to -1	1	8	15	22	29	57	85	113	120	127	134	141	169	197	225	253	281	309	337		365	421	
Lesion count (physician)	X	X	X		X		X	X	X	X		X		X	X	X	X	X	X	X	X		X	X	
Flare assessment ⁴	X	X	X		X		X	X	X	X		X		X	X	X	X	X	X	X	X		X	X	
Numerical Rating Scale for pain assessment ⁵	Completed daily in the eDiary										Completed weekly in the eDiary														
Modified Hidradenitis Suppurativa Score (mHSS)			X							X	X													X	
HS-Physician's Global Assessment				X		X		X	X	X	X						X							X	
Patient's Lesion Count	Completed weekly in the eDiary																								
DLQI				X		X		X		X								X						X	
EQ5D				X		X		X		X								X						X	
Patient Global Impression of severity (PGI-s)			X		X		X		X	X							X							X	
Patient Global Impression of change (PGI-c)			X		X		X		X	X							X							X	
Work productivity Activity Impairment (WPAI)			X		X						X						X			X				X	
HS Symptom Diary ⁶	Completed daily in the eDiary																			X				X	
Hematology	X		X		X		X	X	X	X		X		X		X		X		X			X		
Clinical Chemistry	X		X		X		X	X	X	X		X		X		X		X		X			X		

Period	Screening		Treatment Period 1							Treatment Period 2										Post-Treatment Follow-Up				
	Screening 1	Screening 2	Baseline	Week 1	Week 2	Week 3	Week 4	Week 8	Week 12	Week 16 / EOT1	Week 17	Week 18	Week 19	Week 20	Week 24	Week 28	Week 32	Week 36	Week 40	Week 44	Week 48	UNS 1 to 3	Week 52 / EOT2	
Visit Name																								Week 60 / F8
Days	-28 to -14	-13 to -1	1	8	15	22	29	57	85	113	120	127	134	141	169	197	225	253	281	309	337		365	421

^x Assessment to be recorded in the clinical database or received electronically from a vendor

^s Assessment to be recorded in the source documentation only

¹ These assessments are source documentation only and will not be entered into the eCRF. However, data regarding to which inclusion/exclusion criteria are not met are captured on the Inclusion/Exclusion eCRF.

² While all concomitant medications are recorded on eCRF, patients will record their daily analgesics use on eDiary.

³ AEs /SAEs occurring after the patient has provided informed consent must be reported.

⁴ Occurrence of flare will be calculated from lesion count assessment and does not require any additional action from the site staff.

⁵ Subjects will complete the NRS skin pain assessment using eDiary. From Screening through Week 16, subjects will complete a daily diary of their skin pain. From Week 16 through Week 52, subjects will complete skin pain assessments on a weekly basis.

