12.4.4 Sensitivity and Supportive analyses

Sensitivity analyses

To further support the primary estimand, sensitivity analyses will be considered in the way of varying assumptions about the missing outcomes between treatment arms.

Another sensitivity analysis will be performed where the baseline is defined as weighted average of first screening visit (with weight 1/6) and the second screening visit (with weight 2/6) and the randomization visit (with weight 3/6). This weighted average is being used during the study to identify the need for rescue medication and it is also used at Week 52 to identify responders being randomized in the extension study.

Supportive analyses

A supplementary estimand, which is detailed in the Statistical Analysis Plan, and following analyses will also be done to support primary endpoints:

- The number and percentage of subjects will be presented for proportions of subjects who achieved at least 50%, 75% and 100% reductions in the AN count relative to Baseline (AN50, AN75, AN100).
- Summary statistics will be presented for absolute and percent change from Baseline in AN count.
- Summary statistics will be presented for absolute and percent change from Baseline in number of abscesses.
- Summary statistics will be presented for absolute and percent change from Baseline in number of inflammatory nodules.
- Summary statistics will be presented for absolute and percent change from Baseline in number of draining fistulas.

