12.5 Analysis of secondary endpoints

12.5.1 Efficacy and/or Pharmacodynamic endpoint(s)

The secondary endpoints of this study are planned as follow:

- Percentage change from baseline in AN count at Week 16
- Flare over 16 weeks: Patients who experience at least one flare over 16 weeks. Flare is defined as an at least a 25% increase in AN counts with a minimum increase of 2 AN relative to baseline.
- Pain/NSR30 at Week 16: Patients achieving NRS30 at Week 16, among patients with baseline NRS \geq 3. NRS30 is defined as at least 30% reduction and at least 2 unit reduction from baseline in Patient's Global Assessment of Skin Pain. NRS from baseline to Week 16 is the weekly average score calculated based on the 7 available daily scores: Baseline (Week 0) will be average of NRS score from day -7 to day -1, week 1 will be average of

score from day 1 to day 7, week 2 will be average of score from day 8 to day 14 and so on. For any week with less than 4 diary entries within the week, the weekly average will be recorded as missing.

For the secondary endpoint of percentage change in AN count from baseline to Week 16, an analysis of covariance (ANCOVA) model will be fitted to estimate the treatment differences between the two secukinumab regimens and placebo with treatment group, baseline AN count, Hurley stage, use of antibiotic, geographical region and baseline body weight as covariates.

The analysis method for both flare up to Week 16 and Pain/NRS30 at Week 16 will be the logistic regression: with treatment group, Hurley stage, geographical region, use of antibiotic, baseline body weight and baseline AN counts as explanatory variables for flare endpoints; and with treatment group, Hurley stage, region, use of antibiotic, baseline body weight and baseline NRS as explanatory variables for pain endpoints. Odds ratios will be computed for comparisons of secukinumab dose regimens versus placebo utilizing the logistic regression model fitted. In case of response rates of 0% or of 100% in one of the treatment groups, Fisher's exact test will be applied. Risk difference and confidence intervals for risk difference will be provided.

Testing strategy

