**Table 2-1 Assessment windows for scheduled visits for analyses based on the entire study period**

Analysis Visit	Week	Scheduled Day	Visit Window
Baseline	BSL	1	-28 days to Day 1*
Week 1	1	8	Day 2-11
Week 2	2	15	Day 12-18
Week 3	3	22	Day 19-25
Week 4	4	29	Day 26-43
Week 8	8	57	Day 44-71
Week 12	12	85	Day 72-99
Week 16	16	113	Day 100-120
Week 18	18	127	Day 121-134
Week 20	20	141	Day 135-155
Week 24	24	169	Day 156-183
Week 28	28	197	Day 184-211
Week 32	32	225	Day 212-239
Week 36	36	253	Day 240-267
Week 40	40	281	Day 268-295
Week 44	44	309	Day 296-323
Week 48	48	337	Day 324-351
Week 52	52	365	Day 352-379
Follow up	60	421	Starting from day 380

\* Baseline measurement before the first drug administration.

For HiSCR, HiSCR components inflammatory nodules, abscesses, draining fistulae, Flare and other lesion related assessments, Screening 1 visit, Screening 2 visit and baseline visit will be adjusted per below table

Analysis Visit	Week	Scheduled Day	Visit Window
Screening 1	-4	-21	-28 days to -14 days
Screening 2	-2	-7	-13 days to -1 days
Baseline	BSL	1	Day 1

For parameters which are not collected at every visit (e.g. weight, laboratory parameters, DLQI), visit windows defined in and [Table 2-1](#) will be combined. The following rules are used to determine the visit window for an applicable visit post baseline: “Lower limit” = “upper limit of prior applicable visit” + 1. “Upper limit” = “target day of current visit” + integer part of (“target day of next applicable visit” – “target day of current visit”)/2. For example, if a parameter is measured at Baseline, Week 12 and Week 28 only, Week 12 visit window will extend from Day 2 to Day 141 (combining Week 1 to Week 20 visit windows), Week 28 will extend from Day 142 to Day 379 (combining Week 24 to Week 52). If more than one assessment falls into the interval, the rules defined below are applied.

The analysis visit will be used for listing of visit and period for both safety and efficacy data. If a visit falls after the last visit window (after Day 379) it is not assigned to an analysis visit and will be listed under label “After Week 52”.

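### The Week 16 HiSCR, AN-count and flare models leave out the two screening AN counts; adding their mean as a covariate would be a cheap but modest gain in precision

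*Protocol*

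**What the plan says.** Protocol Section 3 and the lesion-count row of Table 8-1 schedule a physician count at Screening 1, Screening 2 and Baseline. The visit-window section of the SAP (2.5.1.1) keeps these as separate analysis visits for lesion data: "Screening 1 visit, Screening 2 visit and baseline visit will be adjusted per below table".

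Only the last count serves as baseline. Protocol 12.4.1: "The baseline is defined as the last assessment (including unscheduled visits) obtained before/on the day of the first administration of the study treatment".

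The three Week 16 lesion models each contain a single AN term:
- HiSCR (Protocol 12.4.2): "logistic regression with treatment group, geographical region, Hurley stage, use of antibiotic, baseline body weight and baseline AN counts as explanatory variables".
- Percentage change in AN count (Protocol 12.5.1): an ANCOVA "with treatment group, baseline AN count, Hurley stage, use of antibiotic, geographical region and baseline body weight as covariates".
- Flare (Protocol 12.5.1): logistic regression "with treatment group, Hurley stage, geographical region, use of antibiotic, baseline body weight and baseline AN counts as explanatory variables for flare endpoints".

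The screening counts are used elsewhere, but only inside a weighted average with the randomization count. Protocol 12.4.4 plans a sensitivity analysis in which "baseline is defined as weighted average of first screening visit (with weight 1/6) and the second screening visit" (weight 2/6) and the randomization visit (weight 3/6). The same average drives the rescue rule and the selection of responders for the extension study.

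**The concern.** The baseline count is the reference for all three endpoints: the denominator of percentage change, the HiSCR threshold and the flare threshold. A count that is high by chance makes a 50% fall easier to reach; one that is low by chance makes it harder and makes flare easier. The Amendment 2 rationale itself refers to variability and subjectivity in HiSCR. Given the baseline count, the two earlier counts indicate how far it lies from the patient's recent level, so they should carry some further information about Week 16.

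The planned sensitivity analysis does not recover that information for the primary endpoint. It replaces the baseline and so changes who counts as a responder; it does not adjust the same endpoint for prognosis.

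What is at stake is power, mainly for q4w against placebo. That regimen is tested at 1% two-sided, with stated power of 83% for HiSCR and 81% for AN count at 471 patients, and in the testing strategy AN count stands before flare.

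**Working it through.** **Inputs from the documents** (Protocol 12.8, SAP Section 3): 471 patients at 1:1:0.5:0.5, hence 157 per active arm and 157 pooled placebo; alpha 4% (q2w) and 1% (q4w), two-sided; HiSCR 30% vs 50%; flare 35% vs 15%; AN count difference 18, SD 46. Current target about 541, or about 180 per group.

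**Step 1: reproduce the stated power.**
- AN count: SE = 46 × √(2/157) = 5.19, and 18/5.19 = 3.467. Power = Φ(3.467 − 2.054) = 92.1% for q2w and Φ(3.467 − 2.576) = 81.4% for q4w. Stated: 92% and 81%.
- HiSCR with continuity correction: effective n = (157 − 1/0.2)²/157 = 147.2. For q4w, z = (0.2 × √147.2 − 2.576 × √(2 × 0.4 × 0.6)) / √(0.21 + 0.25) = 0.946, power 82.8%. For q2w the same formula gives 93.0%. Stated: 83% and 93%.
- Flare, same method: 97.5% and 92.3%. Stated: 98% and 92%.

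**Step 2: variance cut by formula.** The documents give neither correlation, so both are assumed: ρ between any two pre-treatment counts, and r between each of them and Week 16. With baseline alone the residual variance is proportional to 1 − r². With all three counts it is proportional to 1 − 3r²/(1 + 2ρ). Under equal correlations the mean of the two screening counts captures the whole gain. The ratio is

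k = [1 − 3r²/(1 + 2ρ)] / (1 − r²).

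Example, ρ = 0.7, r = 0.5: k = (1 − 0.75/2.4)/0.75 = 0.917. Treating 46 as the residual SD of the baseline-only model, AN-count q4w power is Φ(3.467/√k − 2.576):

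| ρ | r = 0.3 | r = 0.4 | r = 0.5 |
|---|---|---|---|
| 0.6 | k 0.964, 83.0% | 0.931, 84.6% | 0.879, 86.9% |
| 0.7 | 0.975, 82.5% | 0.952, 83.6% | 0.917, 85.2% |
| 0.8 | 0.985, 82.1% | 0.971, 82.7% | 0.949, 83.7% |
| 0.9 | 0.993, 81.7% | 0.986, 82.0% | 0.976, 82.5% |

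Against 81.4%, every cell but one gains 0.3 to 3.8 points. The exception, ρ = 0.6 with r = 0.5, gains 5.5. The formula describes counts on their own scale, whereas the endpoint is percentage change, so it tends to flatter the gain.

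**Step 3: count simulations.** Log-normal counts (median 11), entry at 5 or more lesions, 157 per arm, rates set to the planned 30/50% and 35/15%, HiSCR represented by a 50% AN reduction alone.
- HiSCR: adding the mean screening count was worth about 1–6% more patients. At ρ = 0.7, r = 0.5, simulated q4w power rose from 86.0% to 87.9%. (It starts above 83% because no continuity correction is involved.)
- Flare: also about 1–6% more patients.
- AN percentage change: variance cut 0–6% in this set and 3–7% in another. A few other assumed settings reached about 10%, still inside the formula's range.

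On the plan's own scale, a 3% cut takes AN-count q4w power to Φ(3.467/√0.97 − 2.576) = 82.7%, and a 7% cut to 84.6%. For HiSCR q4w, 1–6% more patients gives Φ((2.576 + 0.946) × √1.01 − 2.576) = 83.2% up to, with 1.06, 85.3%.

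**Step 4: the current sample size.** At 180 per group before missing data, AN-count q4w power is Φ(3.712 − 2.576) = 87.2%. Cuts of 3% and 7% take it to 88.4% and 89.9%. HiSCR q4w starts at 88.8% and flare q4w at 95.8%, so less remains to be gained.

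**The case against.** The case for leaving the models alone has several parts, and most of it stands as a limit on size.

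- **Considered choice.** Amendment 2 moved from the three-visit average to the randomization count after two regulator letters, and kept the average as a sensitivity analysis. A simple primary model is defensible. But the quoted advice concerns which value is the baseline; it neither bars nor discusses an extra pre-randomization covariate.
- **Stronger gain.** A reader might infer that q4w power would rise to about 92–93%. That needs the Week 16 correlation to equal the pre-treatment one, for example both 0.7 (k = 0.76). Week 16 follows 16 weeks of study, with active treatment in two groups, and nothing in the documents supports equality.
- **Free of cost.** A reader might also infer that the change costs nothing. Screening doubles as the washout and taper period (Protocol Section 3, Table 6-2), so in some patients Screening 1 may reflect prior therapy and correlate less well. The reported odds ratio becomes conditional on one more covariate, and its standard error need not fall; the benefit shows in power and in the risk difference.
- **Existing covariates.** Hurley stage, weight, antibiotic use and region may already explain part of the same variance.
- **Unseen document.** The SAP refers the primary and secondary analyses to a Week 16 plan that was not supplied. It may already use the screening counts, for instance in the imputation model, which Protocol 12.4.3 leaves to the SAP.
- **Week 52.** Extending the covariate to the Week 52 models has no power argument: they are exploratory, use observed data (SAP 2.13) and carry no confirmatory test.

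**Conclusion.** The point holds as an optional, inexpensive improvement. All three Week 16 lesion models omit the screening counts, and the documents give no reason against using them as covariates. A reader might take the omission for an error; the documents show no bias, inconsistency or type I error problem arising from it.

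The gain rests on assumed correlations. A fair statement is about 0–4 power points for the q4w comparisons at 471 patients, most likely 1–3, with only the most favourable corner of the formula going beyond that. It shrinks toward zero if counts are stable between visits or only weakly related to Week 16, and it is smaller at about 541 patients. That increase was made to offset pandemic-related missing data, so the powers in Step 4 are upper values.

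**What to change.** Keep the randomization-visit count as baseline for HiSCR, percentage change and flare. Before unblinding, pre-specify the mean of the available Screening 1 and Screening 2 AN counts as one further continuous covariate, beside baseline AN count, in the HiSCR logistic model, the AN-count ANCOVA and the flare logistic model. State a rule for missing values: use the one available count if the other is missing, and a fixed rule based only on pre-randomization data if both are. Put the same covariate in the multiple-imputation model. First check whether the Week 16 plan already does this; if the sponsor prefers the simpler model, a sentence saying why is enough. If Week 16 data have already been unblinded, the adjusted model can serve only as a supplementary analysis.

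Cost: a wording change in Protocol 12.4.2 and 12.5.1 and the Week 16 plan, one degree of freedom per model, and an odds ratio conditional on one more covariate. No new data are needed, and the Week 52 models can stay as they are.
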